### **10.8 Risks for Women of Childbearing Potential or During Pregnancy**

The risks of treatment with IMM-124E during pregnancy have not been evaluated. Human IgG is known to cross the placental barrier. Therefore, IMM-124E has the potential to cause fetal harm when administered to pregnant women and pre-menopausal women of childbearing potential must follow a medically prescribed birth control regimen or agree to abstinence while participating in the study and for 30 days following the last dose of study drug.

### **10.9 Procedures to be Followed in the Event of Pregnancy**

The subject must be instructed to inform the investigator IMMEDIATELY if she becomes pregnant during the study and seek advice regarding discontinuation of study medication. Whenever possible, treatment should be discontinued. The investigator should report all pregnancies to the Sponsor within 24 hours of becoming aware of the pregnancy. The outcome of pregnancies in a subject enrolled in the study must be reported.

In the event that the study drug is being used to treat an existing medical condition, prior to discontinuing therapy, the investigator should counsel the subject and discuss the risks of continuing study drug dosing and the possible effects on the fetus. Subjects should also be counseled regarding the potential for recurrence of their underlying disease if treatment is stopped and the availability of alternative treatment options.

Monitoring of the subject should continue until conclusion of the pregnancy. The outcome of the pregnancy should be reported to the Sponsor.

## 11. SUBJECT COMPLETION/WITHDRAWAL

### 11.1 Subject Completion

A subject will be deemed to have completed the study once all trial procedures have been conducted. Any AEs or SAEs still ongoing at the time of the Exit Evaluation will be followed in accordance with [Section 10.4](#).

### 11.2 Criteria for Premature Withdrawal from Treatment or the Study

Subjects have the right to withdraw from treatment or the study at any time for any reason. The investigator must make every reasonable effort to keep each subject in the study except where termination or withdrawal is for reasons of safety. The investigator also has the right to withdraw subjects from treatment or the study in the event of intercurrent illness, AEs, pregnancy, treatment failure after a prescribed procedure, protocol violations, administrative reasons or other reasons.

The reasons for withdrawal of the subject must be recorded on the CRF.

The following are also considered justifiable reasons for subject withdrawal:

- The need to take medication which may interfere with study measurements
- Intolerable/unacceptable adverse experiences (see [Section 10.7](#))
- Major violation or deviation of study protocol
- Non-compliance of subject with protocol
- Subject unwilling to proceed and/or consent is withdrawn
- Withdrawal from the study is, in the investigator's judgment, in the subject's best interest
- Pregnancy of female study subject at any time during the study period (if applicable)

It is understood by all concerned that an excessive rate of withdrawals from the study can render the study difficult to interpret. Therefore, unnecessary withdrawal of subjects from the study should be avoided.

Immuron may also decide to stop the study and withdraw all subjects for safety or other reasons.

### 11.3 Withdrawal of Subjects from Study drug

[Section 10.6](#) provides guidance for dose discontinuation of Study drug in the event of AEs or abnormal laboratory values. If a subject permanently discontinues study drug, for example as a result of an AE, subjects should be encouraged to continue participation in the study in order to obtain ongoing measurement of study outcomes to minimize missing data. At a minimum, every attempt should be made to continue to follow the subject until resolution of the adverse event. All subjects who discontinue study medication dosing should be followed for at least 28 days after the last dose of Study drug in order to monitor subjects for possible post-treatment events which may occur after Study drug has been discontinued.

### 11.4 Withdrawal of Subjects from the Study

Should a subject decide to withdraw from the study, all efforts will be made to complete and report the observations as thoroughly as possible.

The investigator should contact the subject either by telephone or through a responsible relative to determine, if possible, the reason for withdrawal. A complete final evaluation at the time of the subject withdrawal should be made with an explanation of why the subject is withdrawing from the study.

If the reason for removal of a subject from the study is an AE or an abnormal laboratory test result, the principal reason will also be recorded on the CRF. Where possible, subjects should be followed until the AE is resolved or the abnormal laboratory test has returned to normal.

### 11.5 Replacement of Withdrawn Subjects

Any subjects who discontinue of their own volition or by a decision of the Investigator are defined as “withdrawals”. Early withdrawals will be replaced to reach the predefined sample size of subjects completing the study.

## 12. STATISTICAL ANALYSIS

The study is a randomized, double-blind, placebo controlled, multicenter Phase 2 trial designed to describe the safety and preliminary efficacy of two IMM124-E dose groups as compared to placebo in a population of subjects diagnosed with NASH. The safety profile will be described by the incidence of treatment emergent adverse events (TEAE) as well as changes in vital signs, and laboratory measurements. Trends in efficacy will be examined primarily via reductions from baseline in liver fat content and serum ALT. Given the exploratory nature of the trial, adjustments for multiple endpoints and/or multiple comparisons will not be made.

The following section describes the general analytic approach to the analysis of the study. Details of the analysis will be provided in a separate Statistical Analysis Plan (SAP) which will be completed prior to any blind break.

### 12.1 Sample Size Determination

The power to detect a difference between placebo and active treatment with respect to changes from baseline in liver fat content and serum ALT has been determined for a sample size of 40 patients per arm. The sample size for the current study is based on a review of the literature to obtain estimates to inform sample size/power calculations. Estimates are based on published results of randomized placebo controlled treatment studies in populations of patients similar to those proposed for this study and in which one or both endpoints have been reported. Fat quantification by MRI, rather than other methods, have been included. (Belfort 2006; Promrat 2010; Ratziu 2008; Sanyal 2010 and Le 2012).

Further, since the endpoint is the *change from Baseline*, plausible estimates of the degree of correlation between pre and post-baseline measurements were also incorporated into the variance estimates. Given the wide range of results observed in the literature, several “what if” scenarios were examined. As such, the current sample size was considered sufficient for the exploratory objectives of the study for the given range of plausible treatment effects and variance estimates. There will be no adjustment for multiple comparisons between the 3 treatment groups.

#### Fat Liver Content Change from Baseline:

The current sample size of 40 subjects per group should yield approximately 85% power to detect a treatment effect of at least -5% with respect to the difference in the mean change from Baseline between one of the IMM-124E treatment groups and placebo assuming a standard deviation (SD) of 7.3% ( $\alpha=0.05$ ; two-tailed; unpaired t-test). The SD of 7.3% for the change from Baseline endpoint was derived assuming 1) SDs of 6% for each timepoint, 2) equal variances in each treatment group and 3) a low to moderate correlation of 0.25 between pre- and post-Baseline measurements.

### 12.2 Analysis Populations

The populations for analysis will be as follows:

#### 12.2.1 Full Analysis Set (FAS) for Primary Assessment of Efficacy

The FAS includes all subjects who received at least one dose of study medication. Only subjects with clear documentation that no study medication was received will be excluded. In the event of treatment allocation errors, subjects will be analyzed for efficacy according to the treatment to which they were randomized.

#### 12.2.2 Safety Analysis Set

The Safety Analysis Set includes all randomized subjects who received at least one dose of study medication. Only subjects with clear documentation that no study medication was received may be excluded. In the event of treatment errors, subjects will be analyzed for safety according to the treatment received.

### 12.2.3 Per Protocol Analysis Set

The Per Protocol Analysis Set includes all subjects who complete 24 weeks of study treatment and have MRI and ALT measured at Baseline and at Week 24 and no major protocol violations, determined prior to break of the treatment blind.

### 12.2.4 Intention-To-Treat (ITT) Analysis Set

The ITT analysis set includes all patients randomized to treatment. An ITT analysis will only be implemented in the event that one or more patients are randomized but do not receive any treatment.

## 12.3 Subject Disposition, Baseline Demographics and Disease Status

Subject disposition will be tabulated by treatment arm and overall and will include the number of subjects randomized, received study drug, withdrawals etc. Subjects for whom treatment unblinding was required, including reason(s) will be included. In addition, demographic and baseline information, including Baseline NAS, diabetes status and concurrent medical conditions, will be summarized and tabulated by treatment group. The purpose of these summaries is to characterize the study population and to describe any baseline imbalances.

## 12.4 Statistical Analysis Plan

A detailed SAP in which all aspects of data analysis will be defined in detail and prepared prior to the blind break.

The SAP will include details of the following:

- Definitions of analysis populations
- Description of any data transformations and data derivations to be used together with rationale and references
- Details of the statistical methods to be conducted, together with methods used to estimate corresponding confidence intervals
- Details of methods for checking the appropriateness of the chosen statistical model
- Discussion of the use of covariates and subgroups
- Discussion of any multiplicity and adjustment procedures to be implemented.
- Methods of dealing with missing values and outliers together with details of any sensitivity analyses to be performed
- Specification of any subgroup or interaction analyses
- Example table and listing shells to indicate the proposed presentation of the data.

## 12.5 Efficacy Analyses

Primary determination of efficacy will be assessed by the measurement and comparison of the change in percentage liver fat by MRI at Week 24 for each treatment group. For each variable, summary tables will be produced by time point and by dose level. All data will be listed and outcomes by treatment, including pooled data for both active treatment groups, will be formally compared. The analysis will include determination of confidence intervals about the treatment group means.

### 12.5.1 Other Efficacy Analyses

Other efficacy analyses to investigate outcomes for secondary efficacy endpoints and including sensitivity analyses will be documented as part of the SAP.

Analysis of primary and secondary efficacy endpoints by diabetes status will be descriptive only.

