	
 
• Mean serum ALT, aspartate aminotransaminase (AST), bilirubin, albumin and gamma-glutamyl transpeptidase (GGT) at Weeks 4, 8, 12, 16, 20 and 24
 
• Proportion of subjects whose ALT at Week 24 is within the normal reference range defined as <math>\leq 19</math> IU/L for women and <math>\leq 30</math> IU/L for men.
 

Exploratory outcome measures	
 
• Mean serum concentrations of: lipopolysaccharide (LPS), C-reactive protein (CRP), cytokeratin (CK)-18 fragments, glucagon-like peptide (GLP)-1 and adiponectin and subsets of inflammatory cytokines: interleukin (IL)-6, IL-1<math>\alpha</math>, IL1<math>\beta</math>, IL-2, IL-3, IL-4 IL-10, IL-13, IL-12, IL-17<math>\alpha</math>, IL-23 interferon gamma (IFN<math>\gamma</math>), Transforming Growth Factor Beta (TGF-<math>\beta</math>) and tumor necrosis factor alpha (TNF<math>\alpha</math>)
 
• Serum metabolomics
 
• Relative levels of regulatory T cells in peripheral blood mononuclear cells (PBMC) samples, including CD4, CD8, CD25, FoxP3, NKT, CD62 and CD69 T cells;
 
• Characterization of the gut microbiome
 
• Explore a dose effect
 

Study design:	This is a randomized, double blind, placebo controlled, 3-arm parallel group, multi-dose, multi-center study.
Study duration / participant:	Up to 45 days for Screening and 24 weeks of treatment.  Subjects terminating study drug will be followed-up post-treatment for 28 days.
Number of participants:	At least 120, randomized 1:1:1  Treatment allocation will be stratified by the following: 
 
• Baseline MRI Liver Fat, according to the following scale: <math>\leq 10\%</math>, <math>10\% < X \leq 20\%</math>, <math>20\% < X < 30\%</math> and <math>\geq 30\%</math>
 
• Diabetic status defined as being normal (HBA1C <math>\leq 6.0</math>) or diabetic (having a diagnosis of Type II diabetes and/or HBA1C <math>> 6.0</math> and <math>\leq 9.0</math> whether or not receiving allowable medication).
 

Study drug:	IMM-124E 600mg tablet
Control group:	Placebo to match
Dose Regimens	Arm A: IMM-124E 600mg three times daily; Arm B: IMM-124E 1200mg three times daily; Arm C: Matching placebo three times daily.  All treatment dose regimens are administered per orally

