7.2 Primary efficacy analyses

The hepatic fat fraction will be summarised and tabulated for the Baseline and Week 24 visits along with change from Baseline by randomised treatment group. Change in hepatic fat fraction from Baseline will be analysed using analysis of variance on the ITT, PP and FAS populations, where the model will include the treatment group and another subgrouping variable. As determined by baseline values, hepatic fat fraction categories ($\leq 10\%$, $>10\% - <21\%$, $\geq 21\% - <30\%$ and $\geq 30\%$), HbA1c group ($< 6\%$ and $\geq 6\%$), and ALT (greater or less than 1.5 x the upper normal limit) will be used to subgroup the analysis populations. Further, data from liver biopsies up to 6 months prior to screening will also be used to subgroup analysis populations based on fibrosis (0-1 vs. 2-3), NAS inflammation (0-1 vs. 2-3), and NAS ballooning (0-1 vs. 2). These will be used in addition to the main effects factors and the two-way interaction of those main effects.

In the primary analysis, any missing data will remain missing. Treatment effects between placebo and each of the active treatment groups within each of the hepatic fat and HbA1c categories will be generated and tested for significant differences between treatment and placebo using pre-specified contrasts.

To examine the effect of treatment within the various levels of these subgroup variables, a mixed models ANOVA will be employed if there are an appropriate number of observations in each cell (created by the crossing of study treatment and subgroup categories) and the data does not differ significantly from a normal distribution. In the event that this is not the case, the data will be ranked in an attempt to normalise it, and pairwise contrasts between treatment groups will be performed using Wilcoxon rank sum tests within each combination of visit and subgroup variable level will be performed. However, if the ranked data is also not normally distributed, a permutation test will be employed whereby the unranked data will be randomly sampled (Lehmann, 2006). No adjustment for multiple testing will be made. See Appendix 1 for more information on both the Wilcoxon rank-sum test and the permutation test.

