7.3 Secondary efficacy analyses

The following analyses of secondary efficacy will be performed on the FAS population. However, if the results for the primary efficacy analysis differ across populations, the ITT and PP populations may also be subject to secondary efficacy analysis. For the analyses detailed in this section and section 7.4, inferential statistical analysis will be performed on the same basis as for the primary endpoint. For those values that are recorded at 3 or more time-points, the baseline value will be included in the repeated measures analysis as a covariate. For analyses with only a baseline and final value, t-tests or Wilcoxon rank-sum tests will be performed depending on the distribution of the data. In addition to this, the mean change from baseline for all relevant variables will be assessed and presented.

Serum concentrations of IMM-214E bovine antibodies (including but not limited to: maximum and minimum observed concentration, area under the concentration-time curve, and (if feasible) elimination half-life) will be summarised and tabulated by visit and time point. Pharmacokinetic coefficients, including but not limited to, maximal and minimal concentration, area under the concentration curve and, if possible, elimination half-life will also be summarised and tabulated with change from Baseline by visit.

Body mass index (BMI), waist circumference and waist:hip ratio with change from Baseline will be summarised and tabulated by visit and treatment group.

HbA1c, glucose and homeostatic model assessment of insulin resistance (HOMA-IR) will be summarised and tabulated with change from Baseline by visit and treatment group.

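### The protocol makes results by diabetes status descriptive only, but the SAP tests each dose against placebo within HbA1c categories and does not declare the change

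*Protocol*

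**What the plan says.** Protocol 12.5.1 limits one kind of subgroup analysis: "Analysis of primary and secondary efficacy endpoints by diabetes status will be descriptive only". The synopsis defines the two diabetes groups by an HbA1c cut at 6.0 and/or a type II diagnosis (the text beginning "Diabetic status defined as being normal"). Section 8.1 describes the matching stratum by HbA1c alone.

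SAP 7.2 says that effects of each dose against placebo "within each of the hepatic fat and HbA1c categories will be generated and tested for significant differences between treatment and placebo using pre-specified contrasts". The next paragraph adds: "To examine the effect of treatment within the various levels of these subgroup variables, a mixed models ANOVA will be employed", with rank-based and permutation methods as fallbacks, and says that multiple testing will not be adjusted for. The listed factors are hepatic fat (four categories) and HbA1c, ALT, fibrosis, inflammation and ballooning (two each). The model also contains the two-way interaction of the main effects.

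SAP 7.3 extends this to the endpoints of sections 7.3 and 7.4: "inferential statistical analysis will be performed on the same basis as for the primary endpoint". The table list in SAP section 12 includes HbA1c subgroup tables for liver fat and for many secondary variables.

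On changes from the protocol, SAP section 3 says only that later changes are included, and SAP section 10 leaves their documentation to the final study report. Neither names this one.

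**The concern.** The protocol allows description by diabetes status and the SAP produces p-values by its counterpart. The SAP is the document the analyst will follow, so significance statements within HbA1c categories will appear in the report although the protocol ruled them out.

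Two things are at stake. First, a chance result in one HbA1c category could be read as evidence in that type of patient. The trial is meant to recommend a dose, and SAP section 9 uses the interim analysis to look for efficacy signals and to set sample size parameters for later studies, so such a result could carry weight. Second, a small p-value in one category does not show that the effect differs between categories; that is a question for the interaction. The same problem of interpretation arises for the other five factors, but the protocol does not restrict those to description.

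**Working it through.** **1. The plan's own figure.** The documents give no error rate for the subgroup tests. Their nearest figure is the power statement in Protocol 12.1. SD of change = √(6² + 6² − 2 × 0.25 × 6 × 6) = √54 = 7.35, stated as 7.3. With 40 per group, a difference of 5 and SD 7.3, a two-sided t-test at 0.05 has 85.7% power, against the stated 85%. The figure reproduces, and 40 per arm is used below.

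**2. Counting tests on the primary endpoint** (one population, one analysis, two doses each against placebo):
- HbA1c: 2 levels × 2 doses = 4.
- Hepatic fat plus HbA1c: (4 + 2) × 2 = 12. These are the only contrasts that SAP 7.2 explicitly says are tested for significance.
- All six factors: (4 + 2 + 2 + 2 + 2 + 2) × 2 = 28. The sample table for the primary analysis with subgrouping (SAP section 12) names all six factors and has group-comparison columns.

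**3. Chance of at least one false positive with no effect.** Under independence this is 1 − (1 − α)^k, with α = 0.04695 from SAP section 9. The tests share patients and a placebo arm, so independence overstates it. Simulated null trials used 40 per arm and contrasts within levels on the pooled residual variance:

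| Tests | Independence | Simulated, either direction | Simulated, favouring drug |
|---|---|---|---|
| HbA1c (4) | 17.5% | about 16% | about 8% |
| Hepatic fat + HbA1c (12) | 43.9% | about 37% | about 20% |
| All six factors (28) | 74.0% | about 56% | about 30% |

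Expected false positives over 28 tests: 28 × 0.04695 = 1.3. At α = 0.05 the simulated either-direction figures are about 17%, 40% and 59%.

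**4. Sensitivity.** The documents give no subgroup prevalences or correlations between factors, so these are assumptions. For 28 tests, over both alpha levels, the result ranges from 52% to 66% across balanced and unbalanced prevalences, factor correlations of 0 to 0.6, and half the biopsy data missing. It falls to 46% to 50% only if the six factors are almost one variable (latent correlation 0.9).

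**5. What remains after a change.** Making HbA1c descriptive leaves 24 tests and about 53% in either direction at α = 0.04695 (about 55% at 0.05). One interaction test for each of the five other factors gives, under independence at 0.05, 1 − 0.95⁵ = 22.6%; simulation gives about 22% to 23%.

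**The case against.** The strongest reply is that this is an exploratory phase 2 trial that says so. The introduction to Protocol section 12 declines adjustment for multiple endpoints and comparisons on that ground, and Protocol 12.4 leaves subgroup and interaction analyses to the SAP. For hepatic fat, ALT, fibrosis, inflammation and ballooning this stands: unadjusted testing there is a declared choice and contradicts nothing. It does not lift the specific limit on diabetes status, which is in the same protocol section.

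It can also be said that HbA1c group is not diabetes status. The SAP cuts at below 6% against 6% or more, while the protocol puts 6.0 in the normal group and adds a diagnosis term. The two are not identical, but the SAP offers no other grouping by diabetes status, so it is the working counterpart.

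A reader might infer that the contradiction makes a false positive subgroup result more likely than not. The documents do not support that. The 56% needs 24 tests that Protocol 12.5.1 does not restrict. It also needs a reading of SAP 7.2 that the sample table supports but the text leaves open, because "To examine the effect of treatment within the various levels of these subgroup variables, a mixed models ANOVA will be employed" could refer to two factors or to six. And it counts results against the drug as well as for it.

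Nor is the interaction missing from the plan; it is in the SAP 7.2 model. Nor do the ITT, FAS and PP repeats multiply the error rate: these populations are largely the same patients, and SAP 3.1 uses the ITT population only if someone was randomised but not dosed.

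**Conclusion.** The contradiction is real and undeclared. Its own size is modest: four tests on the primary endpoint, about a 16% chance of a false positive and about 8% for one favouring the drug, with more from the secondary endpoints, which were not counted. The wider figures describe the unadjusted subgroup programme as a whole and not the breach of the protocol: about 37% for the 12 contrasts explicitly tested, and about 56% in either direction or 30% favouring the drug if all six factors are tested within levels. All assume no treatment effect, 40 evaluable patients per arm and α = 0.04695, with subgroup prevalences that the documents do not give. The overall comparison of each dose with placebo is not affected.

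**What to change.** In SAP 7.2 and 7.3, and in the matching tables, present HbA1c-level results for primary and secondary endpoints as estimates with confidence intervals and no p-values, in line with Protocol 12.5.1.

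For the other five factors, report the treatment-by-factor interaction that the model already contains, next to the estimates and confidence intervals for each level. Label these analyses exploratory and unadjusted, consistent with Protocol section 12, and state that no efficacy claim, dose choice or population choice rests on significance in a single level. The protocol does not require deleting the other within-level tests or restricting subgroup tables to one population.

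The cost is SAP wording and some table changes, to be settled before unblinding; no patients or procedures are involved. The downside is that no HbA1c subgroup p-values can be quoted, and that the five interaction tests, being unadjusted, still carry about a 22% to 23% chance of at least one false positive.
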